Orthopaedic trauma patients treated at Eskenazi (previously Wishard) Hospital, a level 1 trauma center, are routinely allowed to be permissively anemic, or allowed to run as low as a Hemoglobin of 5 g/dL if they are young and healthy (see inclusion/exclusion criteria for objective definition) and asymptomatic from anemia. A retrospective review was performed using the inclusion/exclusion criteria proposed in this study to evaluate if a prospective study would be ethical and to provide a power analysis for number of patients needed to reject the null hypothesis. Over a 3 year period (2006-2009), 104 patients were identified who met the inclusion/exclusion criteria proposed in this study and were available for 1 year follow-up. This study controlled for Injury Severity Score, patient age, gender, and whether the patient had received multiple surgeries. We found that patients who were allowed to be permissively anemic (allowed to drop to a Hgb of 5 g/dL if asymptomatic at rest) had a lower complication rate ($p<0.01$) than those who were transfused to maintain a higher hemoglobin. Additionally, there appeared to be a dose-dependent affect ($p=0.02$) with higher complications seen in patients receiving multiple units of allogeneic blood. This data was presented at both the American Academy of Orthopaedic Surgery (2011) and Orthopaedic Trauma Association (2011) annual meetings and the manuscript is currently being reviewed for publication. This retrospective study does not prove causation of higher complication rates associated directly with transfusion, but does suggest there may be a lower complication rate in patients allowed to be permissively anemic. The largest barrier to publication of this retrospective study has been the repeated comments by reviewers that a prospective study is needed.

[name], Chief of Orthopaedic Trauma at Eskenazi Hospital, has met with the Chief of Anesthesia at Eskenazi Hospital, [name], and the Chief of Trauma for General Surgery, [name], to develop the inclusion and exclusion criteria listed

below so that this study might be completed in a multi-disciplinary approach with all providers agreeing to the inclusion and exclusion criteria and escape criteria listed below.

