8.0 Statistical Considerations

Sample size:

This is a pilot study since the primary purpose of this study is to collect preliminary data on estimating the complication rates for orthopedic trauma patients who will receive blood transfusion either with a liberal transfusion strategy or a conservative strategy. The primary outcome of this study is whether a patient develops a complication while following a

conservative or liberal transfusion strategy for anemia. From our retrospective study, we anticipate the true complication rate would be anywhere between 30% and 50%. We want to estimate this proportion with 95% confidence and no more than 14% margin of error. With a sample size of 50 per group we would be able to reach this goal. For example, if the true proportion is 40%, the margin of error will be 13.6% and the maximum margin of error would be 13.9% when the true proportion is 50%.

Up to 370 subjects will be enrolled as part of the non-treatment group.

Data Analysis:

The primary endpoint is a dichotomous outcome, the presence or absence of a complication at post blood transfusion. A point estimate (sample proportion) and a 95% confidence interval for the proportion will be reported. This proportion will be computed for each of the two blood transfusion strategies. Although we did not power the study to detect a difference in complication rate between two strategies, we will compare the complication rates between two groups of patients. Descriptive statistics, like, mean, median, standard deviation for continuous outcomes will be used to describe the subjects' characteristics at baseline. Frequency counts and percent will be used for the categorical outcomes. Baseline clinical and demographic data will be compared between two groups to assess the effectiveness of the randomization. Dichotomous and ordinal variables will be examined using chi-square tests and continuous measures with Student's t-tests. Exploratory analysis will be performed to compute p-values which will be presented as an aid to evaluate the overall comparability of the treatment groups at baseline. Logistic regression model will be used to compare the complication rate or infection rate between two groups and baseline covariates will be included in the model if two groups are found to be significantly different in those covariates.

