Methods: A retrospective review of 104 patients treated at a level 1 trauma center by a single surgeon from September 2006- February 2009 was conducted. Inclusion criteria were patients 18-50 years of age and a hemoglobin concentration of 9.0 g per deciliter (g/dL) or less at any time during their admission. Patients with head injury, pregnancy, or patients with a pre-existing history of pulmonary, cardiac, or renal conditions were excluded. The patients were initially divided into two cohorts by their lowest hemoglobin level prior to first transfusion of < 7.0 (g/dl) and >7.0 (g/dl); this was followed by further division depending on whether the patients were transfused. Logistic regression analysis was performed. Patients' charts were reviewed for complications extending through a one-year period after initial discharge from the inpatient service. Patients who had not received follow-up treatment through a known outpatient clinic were contacted by telephone to ascertain outcome. Overall, 5 out of 104 patients were lost at one-year follow-up. Among other variables, postoperative complications were recorded as our primary outcome. Superficial wound infection was defined as cellulitis within one year requiring oral antibiotics; deep wound infection was defined as any infection within 1 year of injury which required intravenous antibiotics or surgical debridement in the operating room. Complications included (not all were found but the following were specifically searched) superficial infection (defined as cellulitis requiring oral antibiotics), deep infection (defined as requiring intravenous antibiotics or surgical debridement), urinary tract infection, pneumonia, pulmonary embolism, deep venous thrombosis, acute renal failure or insufficiency, nonunion, delayed union, compartment syndrome, osteomyelitis, nerve palsy, anoxic brain injury, cardiac ischemia or infarct, pancreatitis, or death.

Results: There was no increased risk for complication related to anemia itself ($p=0.3$). However, there was a significant risk for complication related to transfusion ($p<0.01$); furthermore, there was a dose-dependent effect with complication risk increasing with each unit transfused ($p=0.02$). Other factors such as age, injury severity score (ISS), and gender were considered and when adjusted did not change these results.

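### Baseline significance tests choose the covariates for the between-arm logistic model; a short fixed list should replace them

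*Combined protocol and SAP*

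**What the plan says.** Section 8.0, Data Analysis, plans the between-arm comparison as follows: "Logistic regression model will be used to compare the complication rate or infection rate between two groups". The covariates are chosen by a test: "baseline covariates will be included in the model if two groups are found to be significantly different in those covariates".

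The tests are chi-square for dichotomous and ordinal variables and Student's t for continuous ones. Their stated purpose is descriptive. The plan says "Baseline clinical and demographic data will be compared between two groups to assess the effectiveness of the randomization", and it describes "p-values which will be presented as an aid to evaluate the overall comparability of the treatment groups at baseline". The same p-values then decide the model. No significance level, candidate list or fixed covariate set is given there or elsewhere.

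The plan limits the weight of the comparison itself: "Although we did not power the study to detect a difference in complication rate between two strategies". The main analysis is each arm's proportion with a 95% confidence interval. Section 2.0 nevertheless states a null hypothesis of no difference between the strategies, so the contrast will be read.

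On possible covariates, section 1.0 says of the team's retrospective study: "This study controlled for Injury Severity Score, patient age, gender, and whether the patient had received multiple surgeries". Appendix K reports: "Other factors such as age, injury severity score (ISS), and gender were considered and when adjusted did not change these results".

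**The concern.** Section 4.0 assigns arms at random in blocks of 4. If that is done properly, any baseline difference between the arms is chance. A significance filter therefore selects on chance imbalance, and a strong predictor of complications is no more likely to enter than an irrelevant variable. Three things follow.

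- **The model is unknown in advance.** It depends on which variables are tested, at what level, and how the arms happen to fall.
- **Most of the benefit of adjustment is lost.** Adjusting for a prognostic covariate raises power in logistic regression. The rule leaves such a covariate out about 95% of the time.
- **Chance decides what is estimated.** An unadjusted odds ratio and one conditional on covariates are different quantities. The reader would not know before the analysis which will be reported.

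**Working it through.** **The plan's own figures.** The half-width of a 95% interval with n = 50 is 1.96 × √(p(1−p)/50). At p = 0.40 this is 1.96 × √(0.24/50) = 0.136. At p = 0.50 it is 1.96 × √(0.25/50) = 0.139. Both match section 8.0, and the covariate rule does not affect them.

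**Inputs.** From section 8.0: 50 per arm, an anticipated complication rate of 30% to 50%, and the t and chi-square tests. Assumed, because the documents do not give them: a two-sided 5% entry level, the number of candidates, and how strongly each predicts the outcome.

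**Entry threshold.**
- Continuous covariate: t(0.975, 98 df) × √(2/50) = 0.397 SD.
- Binary covariate, uncorrected chi-square: 29/50 against 20/50 gives p = 0.072 and stays out. 30/50 against 20/50 gives p = 0.046 and goes in. One patient changes the model.

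**How often anything enters.** For k independent candidates the chance is 1 − 0.95^k.

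| Candidates | At least one enters | Unadjusted model |
|---|---|---|
| 3 | 14.3% | 85.7% |
| 4 | 18.5% | 81.5% |
| 10 | 40.1% | 59.9% |
| 20 | 64.2% | 35.8% |

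Three candidates already allow 2³ = 8 models.

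**Power.** Simulation used 50 per arm and 20,000 trials per scenario. Age and ISS were independent standard normals, and gender was binary (30/70 assumed) with no effect. Entry was at 5%, with a Wald test of treatment. The table gives power with age and ISS always included minus power under the plan's rule, in percentage points. Columns are the assumed odds ratios per SD of the two covariates. Monte Carlo standard error is at most 0.27 points.

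| Scenario | 1.0, 1.0 | 1.5, 1.0 | 1.5, 1.5 | 2.0, 1.5 | 3.0, 1.5 |
|---|---|---|---|---|---|
| Control 30%, log-OR −1 | 1.0 | 2.0 | 2.7 | 4.7 | 7.1 |
| Control 40%, log-OR −1 | 1.0 | 2.2 | 3.3 | 5.5 | 9.0 |
| Control 50%, log-OR −1 | −0.1 | 0.8 | 2.2 | 4.0 | 7.7 |
| 50% against 30% | −1.0 | 0.7 | 1.8 | 3.7 | 7.6 |

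With log-OR −1 the other arm falls to 14–16%, 20–23% and 27–31% in the first three rows. The fourth row keeps both arms inside the plan's range. In the first two rows about 1 point of each gap appears even when the covariates predict nothing, so that part is not a prognostic gain. The rule stayed within 0.6 points of no adjustment throughout.

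**Mechanism**, at 40% control with odds ratios 2.0 and 1.5:

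| Model | Mean log-OR | Mean SE | Power |
|---|---|---|---|
| Unadjusted | −0.911 | 0.459 | 50.0% |
| Plan's rule | −0.918 | 0.463 | 50.0% |
| Fixed list | −1.054 | 0.505 | 55.4% |

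The standard error rises with adjustment, but the estimate moves further from zero. This is a gain in power, not in precision.

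**Longer candidate list.** A second simulation used 5,000 trials per scenario, ten candidates of which three made up the fixed list, and a conditional treatment odds ratio of 2.33. Power for unadjusted, rule and fixed list was 54.9%, 53.5% and 53.6% with no prognostic value. It was 46.8%, 45.6% and 48.8% at odds ratio 1.5 per SD, and 37.8%, 36.1% and 43.3% at 2.0. With ten candidates the rule fell 1.2 to 1.7 points below no adjustment.

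**Type I error.** Over nine null scenarios of the first simulation: unadjusted 4.3–5.8%, rule 4.0–5.7%, fixed list 4.5–5.3%. The rule does not inflate it.

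**The case against.** The best case for leaving the text alone is that little is at stake. This is a pilot aimed at estimating rates, and the comparison is declared unpowered. In the two scenarios at or near the plan's 30% to 50% range, a fixed list changes power by −0.1 and −1.0 points with no predictive covariates, and by +0.8 and +0.7 with one weak predictor. The larger gains need odds ratios of 2.0 to 3.0 per SD, which nothing in the documents supports. Age is limited to 18–50, and adjustment did not change the retrospective results. That stands, although an unchanged treatment effect after adjustment does not measure how well a covariate predicts outcome.

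The choice of three candidates is also an assumption. With 10 or 20, the share of unadjusted models falls from about 86% to about 60% or 36%. The rule is then less predictable, which strengthens the case against it.

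The fix has practical limits too. No form in Appendices A–I has a field for ISS or gender. If ISS carries the signal, falling back on age and gender recovers little. In a check of 4,000 trials (40% control, log-OR −1, ISS odds ratio 1.5, age and gender null), power was 58.0% under the rule, 60.0% with age and ISS, and 58.6% with age and gender. Events may also be few: the first two scenarios yield only about 22–23 and 30–32 in 100 patients, and no infection-specific rate was simulated.

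Finally, the per-arm proportions always allow an unadjusted contrast. That softens the problem of mixed quantities, but the odds ratio from the model would still vary in meaning. None of this is a reason to select covariates by baseline tests.

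**Conclusion.** The concern holds and its weight is modest. The rule lets chance set the model and, with three candidates, performs within 0.6 points of no adjustment. The certain loss is a model that can be stated in advance. The possible loss is power: nothing to about 3 points if the covariates are weak predictors, which is the more realistic case, and 3.7 to 9.0 points if one is strong. If they predict nothing, a fixed list could cost about 1 point. These figures rest on the assumed 5% entry level, independent covariates, the assumed effect sizes and, for the main table, three candidates. The per-arm estimates, their intervals, the sample size and type I error are unaffected. Prespecification alone justifies the change.

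**What to change.** In section 8.0, replace the selection rule with text such as: *The between-arm logistic model includes treatment arm, age and Injury Severity Score at randomization, regardless of observed balance. The unadjusted comparison is reported as a sensitivity analysis. If ISS capture cannot be confirmed before the arms are compared, age and gender are used instead.*

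Also state:

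- how a missing ISS is handled, for example by the mean over both arms;
- that the adjusted odds ratio is conditional and differs from the contrast of the per-arm proportions;
- that baseline tests, if kept, are descriptive only and do not select covariates;
- optionally, a Firth penalty if infection events are few.

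Age and ISS are suggested because the team controlled for them before, not because they are shown to be prognostic. Multiple surgeries, also on the retrospective list, qualifies only if restricted to surgery before randomization. Which outcome is primary (sections 2.0, 5.0 and 8.0) is a separate matter.

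The cost is wording plus a data check. Age follows from the date of birth in Appendix B. ISS or gender must be confirmed as available from the hospital record. Two covariates use two degrees of freedom against the 30 to 50 complications implied by the plan's rates in 100 patients. Sample size and visits do not change.

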9.0 Privacy/Confidentiality Issues

Standard HIPAA practices will apply to all sensitive data recorded for study purposes. All attempts will be made to maintain confidentiality between study participants and the research team. Computer/files will be password protected, kept behind locked doors, and located in an area with no public access.

10.0 Follow-up and Record Retention

Duration of the study will last approximately 3 years or until 100 patients have been enrolled with one year follow-up and all necessary data has been collected and analyzed.

Upon study completion, records will be retained for a minimum of 7 years as required by state law. After mandatory retention period, sensitive information will be disposed of by means of hospital provided secure document disposal.

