4.0 Enrollment/Randomization

A consensus opinion was reached in a multidisciplinary manner with multiple members of the Trauma team (General Surgery), Anesthesia, Physical Medicine and Rehab, and the Orthopaedic Trauma Service. This team consisted of members from General Surgery ([name], [name], [name], [name]), Anesthesia ([name], [name], [name]), and Physical Medicine and Rehab ([name]) along with all members of the Orthopaedic Trauma Service ([name], [name], [name]) and the PI ([name]). The opinions in escape criteria and definitions will be referred to below as "consensus opinion". A biostatistician was consulted after he had reviewed the data from the retrospective study previously performed at this institution to help design an appropriately powered prospective randomized pilot study.

All Orthopaedic Trauma patients admitted to participating hospital will be screened for inclusion and exclusion criteria after they have been resuscitated and stabilized. The consensus opinion of the "stable" patient was defined as an awake and alert patient with normal urine output and systolic blood pressure greater than 90 mmHG for greater than 6 hours without fluid bolus or resuscitation. If a patient meets criteria for the study as noted above and is stable as defined above, the patient would be approached by either the Principal Investigator (PI) or a co-PI to determine interest and informed consent would be obtained for participation in the study. Patients who either refuse or are unable to consent will be tracked using the screening form. Enrollment would be performed in patients with a Hgb of 9 g/dL or less or in patients expected to drop below 9 g/dL with planned procedures or continued (controlled) bleeding. Randomization would not occur until the patient's Hgb dropped below 7 g/dL at which time a sealed envelope would be opened to determine if the patient would be randomized to a liberal transfusion strategy (transfuse to keep Hgb >7 g/dL) or a conservative strategy (transfuse to keep Hgb > 5.5 g/dL). If the patient's Hgb does not drop below 7.0 g/dL, randomization will not be done. Prior to starting enrollment, envelopes will be made by blinded personnel using a randomization list generated to assign subjects to receive treatment either after hemoglobin drops below 5.5 or after hemoglobin drops below 7.0. Randomization was

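### Could the three-year clause in Section 10.0 close the trial below 50 randomised patients per arm?

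*Combined protocol and SAP*

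**What the plan says.** Section 10.0 (Follow-up and Record Retention) reads: "Duration of the study will last approximately 3 years or until 100 patients have been enrolled with one year follow-up". The sentence goes on to require that the data be complete and analysed. It does not say whether the earlier or the later condition applies.

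Section 8.0 gives the reason for the number. The aim is a 95% margin of error of no more than 14% for a complication rate between 30% and 50%: "With a sample size of 50 per group we would be able to reach this goal". A separate cohort is counted apart from these: "Up to 370 subjects will be enrolled as part of the non-treatment group". Section 8.0 contains no time limit.

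The documents give one count of patients over time, from the retrospective series. Section 1.0 says: "Over a 3 year period (2006-2009), 104 patients were identified who met the inclusion/exclusion criteria proposed in this study". Appendix K describes the series as "104 patients treated at a level 1 trauma center by a single surgeon from September 2006- February 2009", selected on "a hemoglobin concentration of 9.0 g per deciliter (g/dL) or less at any time during their admission". Section 4.0 sets a narrower condition for randomisation, which waits until the patient's "Hgb dropped below 7 g/dL at which time a sealed envelope would be opened". It also foresees refusals: "Patients who either refuse or are unable to consent will be tracked using the screening form".

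**The concern.** At first sight, 100 patients in three years looks like a restatement of 104 patients in three years. The 104 differs from what the trial needs in three ways. They were selected at a haemoglobin of 9.0 g/dL or less, while randomisation needs a value below 7 g/dL. They passed through no consent step. And their count leaves no room for a year of follow-up after the last patient enters.

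If the trial recruited no faster than that series, three years would arrive before 100 randomised patients. Someone who took the three years as a closing date would then stop below 50 per arm and miss the 14% goal, while someone who took the 100 as governing would carry on. Precision is the only stated reason for the sample size, so the order of the two conditions could decide whether the trial meets its own aim. Section 10.0 also speaks of patients enrolled, and Section 8.0 uses the same word for the non-treatment group, so the 100 could be read as including patients who were never randomised.

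**Working it through.** **The plan's own figures.** Margin = 1.96 × √(p(1 − p)/n), with n = 50 from Section 8.0:

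- p = 0.30: 12.7%
- p = 0.40: 13.6% (stated: 13.6%)
- p = 0.50: 13.9% (stated: 13.9%)

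The stated figures reproduce. The smallest n that meets 14% at p = 0.50 is 49, so 50 has little slack at that rate.

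**Accrual at the retrospective rate.** September 2006 to February 2009 is 30 months (Appendix K); Section 1.0 calls the period three years.

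- 104/30 = 3.47 per month
- 104/36 = 2.89 per month

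**If the three years include the last patient's follow-up** (an assumption), accrual lasts 36 − 12 = 24 months:

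- 104/30 × 24 = 83.2, so 41 per arm. Margins at p = 0.30, 0.40 and 0.50 are 14.0%, 15.0% and 15.3%.
- 104/36 × 24 = 69.3, so 34 per arm. Margins are 15.4%, 16.5% and 16.8%.

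These figures suppose that everyone consents and everyone is randomised. Reaching 100 at these rates would take 28.8 to 34.6 months of accrual, or 40.8 to 46.6 months with follow-up.

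**If all 36 months are available for accrual**, the same rates give 104/36 × 36 = 104 and 104/30 × 36 = 124.8. Both exceed 100. To randomise 100 of them, 100/124.8 = 80% to 100/104 = 96% would have to consent and fall below 7 g/dL.

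**Share falling below 7 g/dL.** The documents do not give it. For assumed shares of 25%, 50% and 75% of the 83.2, the series rate gives 20.8, 41.6 and 62.4 randomised in 24 months, that is 10, 20 and 31 per arm, with margins at p = 0.50 of 31.0%, 21.9% and 17.6%.

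**Accrual the trial would need.** To randomise 100 in 24 months with full consent, the multiple of 3.47 per month is 100/(83.2 × share):

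- share 100%: 1.2
- share 75%: 1.6
- share 50%: 2.4
- share 25%: 4.8

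At an assumed 60% consent these become 2.0, 2.7, 4.0 and 8.0.

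**Whether the series rate applies.** It comes from one surgeon at one centre. Section 4.0 screens all orthopaedic trauma admissions and names several members of the service, and Section 6.0 refers to several participating sites. The plan allows for up to 100 + 370 = 470 subjects. Enrolling them all over 36 months would mean 13.1 per month, 3.8 times the series rate. The 370 is a maximum and enrolment criteria are wider than those of the series, so this is no forecast of randomisations. It does show that the sponsor was not planning around one surgeon's volume.

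**The passages side by side.** Section 8.0 sets 50 per group and counts the non-treatment group separately, so 100 in Section 10.0 can only be 2 × 50 randomised patients. Section 10.0 gives an approximate period and ties completion to follow-up, data collection and analysis. The only power to end the study early stated in the documents is the safety board's in Section 6.0. Nothing tells the sponsor to stop recruiting on a date.

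**The case for a change.** The best case for a change is that the text leaves the choice open, and that the choice would be made while the trial runs. Data are reviewed every six months and the lead investigator hears of adverse events as they occur, so a rule fixed in advance would remove any suspicion that stopping or continuing followed the results. Reserving a year for follow-up is a reasonable reading of a study duration. Without it, 80% to 96% of the series' patients would still have to be randomised to reach 100 at that rate, although the series included patients whose lowest value before transfusion was above 7.0 g/dL. The remedy would cost only a few words.

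Much of this stands. The conditions are unranked, enrolled is looser than randomised, and the plan shows no accrual projection. What does not stand is the step from there to a missed target. The figure of 83 is not a ceiling for this trial: it applies one surgeon's volume to a multi-site study and deducts a year that the sentence does not mention. Even the 104 is uncertain as a rate, since Section 1.0 describes these patients as available at one year while Appendix K reports 5 of them lost. A slow-recruiting trial may close short under any wording, and the number reached and its confidence interval would then show the precision obtained.

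**Conclusion.** The concern does not call for a change. Read together, Sections 8.0 and 10.0 have one workable meaning: recruit until 100 patients, 50 per arm, have been randomised, follow them for a year, and expect this to take about three years. On that reading the largest margin is 13.9% and the 14% goal is met.

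The adverse figures, 15.3% to 16.8% at a 50% rate, need three things together: the three years must act as a cut-off, they must contain the last year of follow-up, and the whole trial must recruit no faster than one surgeon did. They already assume full consent and that every patient is randomised; a lower share would widen the margin at that rate. The documents support neither the first nor the third condition, and they do not give the trial's accrual, so they cannot show that it would fall short. At 41 per arm the excess over 14% is nil to 1.3 points across the anticipated 30% to 50% rates, in a pilot that Section 8.0 says was not powered to compare the arms. What remains is missing detail about wording and feasibility.

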5.0 Study Procedures

If the patient remains asymptomatic at rest (defined as no chest pain, shortness of breath, or dizziness), transfusion would be determined by randomization to the liberal transfusion strategy to maintain Hgb at 7 g/dL or the conservative transfusion strategy of 5.5 g/dL. After each unit of blood is transfused a Hgb level would be checked to ensure appropriate Hgb levels are maintained as well as routine clinical practice (typically daily Hgb levels drawn until at least 2 consecutive days show no further drop with no further procedures or bleeding expected). If the patient's Hgb does not drop below 7.0 g/dL, randomization will not be done but patient will still be followed and patient outcomes will be collected as part of a non-treatment group.

As noted in Section 4.0, a consensus group consisting of multiple physicians and the service chiefs from the Trauma Service (General Surgery), Orthopaedic Trauma Service, Anesthesia, and Physical Medicine and Rehab agreed to the following escape criteria to transfuse regardless of Hgb level or arm of randomization:

Escape Criteria

1. Patient has any of the following symptoms at rest: chest pain, shortness of breath, dizziness
2. Patient has a mean arterial pressure less than 50 mmHg that is not responsive to fluid resuscitation
3. At any time the patient's heart rate increases by more than 30% above baseline while under anesthesia
4. The patient's urine output drops to less than 0.5 mL/kg/hour and remains decreased despite adequate rehydration with fluids
5. Any objective evidence of cardiac ischemia including the following: EKG changes such as ST depression, an elevation of serum cardiac markers, a base deficit greater than 6, lactate greater than 2.5 that does not respond to fluid resuscitation
6. A decrease in systolic blood pressure by 10% or more with exercise (physical therapy) that does not improve with fluid resuscitation
7. Uncontrolled source of hemorrhage

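### Section 10 sets completion at 100 patients enrolled, but in this plan enrollment precedes randomization and includes up to 370 never-randomized patients; the count should be 100 randomized

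*Combined protocol and SAP*

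**What the plan says.** - **Completion (Section 10.0).** The study is to run for about 3 years or "until 100 patients have been enrolled with one year follow-up and all necessary data has been collected and analyzed".
- **Entry (Section 4.0).** "Enrollment would be performed in patients with a Hgb of 9 g/dL or less or in patients expected to drop below 9 g/dL", the fall being anticipated from planned procedures or continued controlled bleeding.
- **Randomization (Section 4.0).** This is a later, conditional step: "Randomization would not occur until the patient's Hgb dropped below 7 g/dL".
- **Patients who never reach that level (Section 5.0).** They stay in the study: "randomization will not be done but patient will still be followed and patient outcomes will be collected as part of a non-treatment group".
- **Sample size (Section 8.0).** For a 95% margin of error of at most 14% on each strategy's complication rate: "With a sample size of 50 per group we would be able to reach this goal". The next paragraph adds: "Up to 370 subjects will be enrolled as part of the non-treatment group".
- **Screening form (Appendix A).** Enrollment status is recorded against the entry criteria, including hemoglobin below 9 or expected to fall below it. The form has no item for randomization.

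**The concern.** Sections 4, 5 and 8 and Appendix A all treat enrollment as the earlier step, one that takes in patients who may never be randomized. Section 10 then measures completion by enrollment. The only 100 that the sample-size section supports is twice 50, which is a count of randomized patients. The one passage that says when the study is complete therefore counts a different event from the one the sample size rests on.

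Per-arm precision is at stake. Section 8 says the study is not powered for a difference between strategies, so the 14% margin is the only quantitative justification for its size. Anyone who closed recruitment on the Section 10 count, using the word as the rest of the protocol uses it, would have fewer than 50 per arm whenever any of the 100 had not been randomized.

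**Working it through.** **1. Reproduce the plan's figure.** Inputs from Section 8: n = 50 per arm, 95% confidence, anticipated rate p between 30% and 50%. The formula is margin = 1.96 × √(p(1−p)/n).

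- p = 0.30: 1.96 × √(0.21/50) = 12.7%
- p = 0.40: 1.96 × √(0.24/50) = 13.6%
- p = 0.50: 1.96 × √(0.25/50) = 13.9%

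The last two match Section 8. The smallest n for a 14% margin is 1.96² × p(1−p)/0.14², which gives 42, 48 and 49 per arm at 30%, 40% and 50%. So 50 per group is right for its purpose, with little to spare at a 50% rate.

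**2. Compare the counts without assuming anything about the mix.** Section 8 requires 2 × 50 = 100 randomized and allows up to 370 more who are enrolled but not randomized, so total enrollment may reach 100 + 370 = 470. Section 10 is satisfied at 100 enrolled. A group of 370 cannot fit inside a total of 100. Fifty per arm fits only if every enrolled patient is randomized, which leaves no non-treatment group at all.

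**3. Size the gap, conditionally.** The documents do not say what fraction of enrolled patients will be randomized. Let N be the number of non-treatment patients accompanying each 100 randomized, and assume that recruitment closes at 100 enrolled. Then:

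- randomized among 100 enrolled = 100 × 100/(100 + N)
- per arm = half of that, with 1:1 allocation
- margin as in step 1, with unrounded per-arm numbers

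| N | Randomized | Per arm | Margin at 40% | Margin at 50% |
|---|---|---|---|---|
| 0 | 100 | 50 | 13.6% | 13.9% |
| 100 | 50 | 25 | 19.2% | 19.6% |
| 200 | 33 | 16.7 | 23.5% | 24.0% |
| 300 | 25 | 12.5 | 27.2% | 27.7% |
| 370 (cap) | 21 | 10.6 | 29.4% | 30.0% |

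**4. Find where the 14% goal is lost.** At a 50% rate, 49 per arm means 98 randomized. Setting 100 × 100/(100 + N) = 98 gives N = 2.04, so any N above 2 misses the goal. At a 30% rate, 84 randomized are needed and N = 19.05, so any N above 19 misses it. The conclusion does not depend on the non-treatment group being anywhere near its cap.

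**The case against.** The strongest reply is that Section 10 is not a stopping rule. It sits under follow-up and record retention, gives an approximate duration, and offers 3 years as an alternative. Sample size is fixed in Section 8. Since 100 is 2 × 50, the authors very probably meant 100 randomized, and closing at 100 enrolled would make the allowance of 370 pointless. On this view the problem is one loose word.

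Most of that stands, and it rules out two stronger readings that a reader might infer.

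- **That the plan expects 470 enrolled.** It does not. The 370 is a ceiling and no expected total is given.
- **That the study as written stops with about 21 randomized.** This does not follow. The figure needs the non-treatment group to fill its cap and recruitment to close at the 100th enrollment. Section 10 asks for one-year follow-up and completed analysis as well, and never says that recruitment closes at 100. Further patients could be enrolled and randomized while the first 100 are followed.

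Probable intent does not remove the conflict, however. Section 10 is the only statement of when the study is complete, and the rest of the protocol tells staff and the IRB that enrolled patients include those never randomized. A reader has to override the protocol's own usage to reach the intended meaning.

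**Conclusion.** The point holds as an inconsistency in the completion count. Section 10 counts enrolled patients, whereas the sample size in Section 8 is 100 randomized, with up to 370 non-treatment patients in addition. The two cannot both be met as worded, and this needs no assumption about the mix.

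The effect on precision is conditional. If recruitment closed at 100 enrolled, the margin at a 50% rate would run from about 19.6% to 30.0% as the non-treatment group per 100 randomized goes from 100 to the cap of 370. A smaller group would give a smaller gap. These figures rest on the closing assumption, on 1:1 allocation, and on the plan's own normal-approximation formula, which is rough at 10 to 13 per arm. They are not a forecast of what the trial will do. The sample-size calculation itself is sound.

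**What to change.** In Section 10, replace the completion clause with: *until 100 patients have been randomized (50 per arm) and followed for one year*. Add a sentence stating that the non-treatment group, up to 370 patients, does not count toward the 100.

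It would also help to state the fraction of enrolled patients expected to be randomized, so that the ceiling of 370 can be judged against the 100.

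The cost is a sentence or two in a protocol amendment. The planned size, the arms and the analysis are unchanged.
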